7.2.2 Exclusion criteria

Substudy 2A

- Individuals with a diagnosis of seizure, epilepsy, or prescriptions of antiepileptic medicine before entering the study period, as they have prevalent disease.
- Individuals with a diagnosis of malignant brain tumor or head trauma before the first seizure, as they are at high risk of seizures due to causes other than DL use.

Substudy 2B

- Individuals with a diagnosis of seizures, epilepsy, prescriptions of antiepileptic medicine, malignant brain tumor, or head trauma before redemption of first DL prescription, as they have prevalent disease or are at high risk of seizures due to causes other than DL use.
- Individuals with a brain tumor (benign and malignant), initiation of treatment with antiepileptic medicine, or head trauma occurring after beginning of DL use will be censored at date of first occurrence, as they are at high risk of seizures due to causes other than DL use.

Substudies 3A and 4A

- Individuals with a diagnosis of SVT or A-fib/flu before entering the study period, as they have prevalent disease.
- Individuals with a diagnosis of congenital pre-excitation syndrome (e.g., Wolff Parkinson White) before entering the study period, as they are at high risk of cardiac SVT or A-fib/flu due to causes other than DL use.

Substudies 3B and 4B

- Individuals with a diagnosis of SVT or A-fib/flu before use of DL, as they have prevalent disease.
- Individuals with a diagnosis of congenital pre-excitation syndrome (e.g., Wolff Parkinson White) before use of DL, as they are at high risk of SVT or A-fib/flu due to causes other than DL.

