7.3.2 Outcomes

Three outcome variables will be used in the present study: first seizure (Substudy 2B), first SVT (Substudy 3B), and first A-fib/flu (Substudy 4B). Except where noted, the case definition of seizure excludes febrile seizure, a condition in infancy and early childhood attributed to fever. However, supplementary analysis 2 will evaluate the outcomes of febrile and non-febrile seizures in children. (The diagnosis of febrile seizure is generally not used in adults.) Information on outcome variables will be obtained from the Nordic national patient registers, including diagnostic and treatment information for patients treated at the secondary and tertiary hospital level in all four Nordic countries using International Classification of Diseases (ICD)- 10 codes. We will exclude seizure cases if they are registered with brain tumor (benign and malignant), stroke, or acute drug intoxication or overdose of drugs during the same hospitalization as the seizure. [Table 2](#) gives an overview of the outcome variables in the study. For all outcome variables, we will include the primary diagnoses from the emergency room or inpatient settings registered in the Nordic national patient registers.

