7.3.4 Other variables

We will also obtain information on immigration and emigration, as well as date of birth and death status from the civil registration systems to be able to calculate the IRs in Substudies 2B, 3B, and 4B.

The interpretation of register-based variables with regard to missing information was discussed in section 7.3.1 and 7.3.2. For a few of the included register-based variables (e.g., sex and date of birth), all included persons should have information. We do not expect missing information on these variables; however, we will examine data to see whether missing information occurs. Missing data handling will be determined after review of the data, but before data from different registers are linked together (blinded to exposure to DL and outcome status) and will be described in a data control report, which will be submitted along with the study report.

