7.7.1 Substudy 1: Descriptive analysis of exposure of DL

A cohort study describing DL use in the general population will be performed. A person with prescription redemption of DL in Norway and Sweden within the first 6 months after establishment of the prescriptions registers will not be included in order to avoid left-truncation bias. In addition, to avoid analogous misclassification of prevalent with incident DL dispensings among immigrants, we exclude persons with DL prescription redemptions within 6 months after immigrating to Denmark, Finland, Norway, or Sweden. Prevalent users will be defined as persons who have at least one prescription of DL in the period of interest (e.g., the entire study period or each year). Incident users are first time users of DL in the period of interest. The following descriptive analyses will be performed:

- The distribution of prevalent and incident users in the total population and stratified by country, age, sex, calendar year, seasonality, severity of rhinitis, asthmatic status, and chronic urticaria status.
- Descriptive information on the mean, standard deviation, median, and maximum and minimum number of redeemed DL prescriptions in the total population and stratified by country, age, sex, calendar year, seasonality, severity of rhinitis, asthmatic status, and chronic urticaria status.

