A cohort study among ever-DL users analyzing the association between exposed and unexposed time and first seizures will be performed for the total population and stratified by age. Current use (i.e., “exposed” period) will be defined for each prescription as days’ supply plus a 4 week grace period to account for intermittent use and a possible wash-out effect. Unexposed time will be defined as the period starting 26 weeks from the dispensing date of the prior DL prescription until the next DL prescription redemption, if any. A person who has redeemed at least one prescription of DL is included in the cohort and enters the cohort at the date of first prescription redemption. Study individuals are followed until occurrence of a seizure; occurrence of one of the conditions described in section 7.2.2; 31 December 2015; emigration; or death, whichever comes first. The association between exposure to DL and first seizure will be evaluated using Poisson regression of the IR of first seizure, and the measure of effect is the IRR. A person with prescription redemption of DL in Norway and Sweden within the first 6 months after establishment of the prescriptions registers will not be included in order to account for truncation bias. In addition we exclude persons with DL prescription redemptions within 6 months after immigrating to Denmark, Finland, Norway, or Sweden. The analyses will be adjusted for confounders identified from the DAG (i.e., country, age, sex, calendar year, seasonality, severity of rhinitis, asthmatic status, and chronic urticaria status) (Table 4). We will evaluate whether age can be included as a continuous variable by examining the assumption of linearity. Alternatively, age will be included as a categorical variable.

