- Left-truncation is a potential bias in the study meaning that we have no information on DL use before the start of registration of prescriptions in each country. Left-truncation bias in relation to DL use is only a relevant issue for Sweden and Norway since DL was available from 2001, but the prescription registers in Norway and Sweden were established in 2004 and 2005, respectively (Table 4). Therefore, we do not know whether a DL user in the first year of registration in Norway and Sweden is a long-term user (prevalent user) or a first-time user (incident user). To account for this potential bias, a person with prescription redemption of DL in Norway and Sweden within the first 6 months after establishment of the prescriptions registers will not be included. This is not a limitation in Denmark and Finland since DL was first approved in 2001 and the prescription registers in Denmark and Finland were established in 1995 and 1994, respectively. However, left-truncation bias might also occur when persons are immigrating into the study population. Therefore we also exclude persons with DL prescription redemptions within 6 months after immigrating to Denmark, Finland, Norway, or Sweden.
- There is a possibility that patients could purchase DL over-the-counter; however, because of reimbursement systems in the Nordic countries, it is actually less expensive to purchase prescription DL. In Norway and Sweden DL has only been allowed for prescription sale; However, in Denmark, DL has been available for over-the-counter sale since 2013, but over-the-counter sales only counted for less than 4 % of the total amount of DL purchased in 2013. A supplementary analysis will examine the associations under consideration restricting the time period to include only years where DL was not allowed for OTC sale.
- Loratadine, the parent compound of DL, is also available via prescription and over-the counter in the Nordic countries. We think it is somewhat unlikely that patients would switch between DL and loratadine. However, it is possible that some of the time counted as unexposed in the analyses could actually be time exposed to loratadine or over-the-counter DL. Moreover, other non-sedating prescription antihistamines are available in the Nordic countries, and if the effect on the outcomes

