is driven by non-sedating prescription antihistamines in general, rather than the specific effect of desloratadine exposure only, these drugs should be examined to elucidate potential misclassification of exposure. To explore exposure misclassification (i.e., the influence of loratadine and other non-sedating prescription antihistamines on the associations under study), we will conduct supplementary analyses, which will be specified in the statistical analysis plan.

Outcome: Episodes of seizures, SVT, and A-fib/flu

- Seizures, SVT, or A-fib/flu not registered with a relevant diagnosis code in the national patient registers will not be included in the study. However, the completeness of registration is assumed high, since both a procedure for data control of information in the national patient registers is established, and hospitals have an incentive to register patients, as the financing of hospitals is based on the registration of patients treated and procedures performed. If under-recording exists, it would reduce the number of outcomes evaluated, but this under-recording is not likely to be differential (i.e. associated with periods of use or nonuse of DL) and introduce bias.
- The coverage of calendar years in the national patient registers differ between the Nordic countries and may be insufficient to capture the complete history of seizures, SVT, or A-fib/flu at the individual level. Regarding seizures, recurrent seizures would be studied as primary seizures, if first seizure happened before start of registration.
- Truncation is a potential bias in the study meaning that we have no information on seizures, SVT, and A-fib/flu before the start of registration of each of these variables. For Denmark, Finland, and Sweden, information on seizures, SVT, and A-fib/flu is available from 1977, 1967, and 1987, respectively. Thus, the impact of truncation bias on results from these countries is limited. However, information on seizures, SVT, and A-fib/flu in Norway is only available from 2008, which limits the study period of the Norwegian data further and increases the risk of truncation bias.

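### The 6-month immigrant rule washes out desloratadine dispensings only, so an immigrant can enter with little more than 6 months of outcome history, and its wording can delete a returning resident's earlier person-time

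*Protocol*

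**What the plan says.** **The rule.** Sections 7.7.2, 7.7.3 and 7.7.4 each state: "In addition we exclude persons with DL prescription redemptions within 6 months after immigrating to Denmark, Finland, Norway, or Sweden". Section 7.7.1 gives its purpose: "to avoid analogous misclassification of prevalent with incident DL dispensings among immigrants". Section 7.9 repeats the reasoning under the exposure heading, where it notes that "left-truncation bias might also occur when persons are immigrating into the study population".

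**Outcome history.** This is handled separately, in section 7.2.2. Substudies 3B and 4B exclude "Individuals with a diagnosis of SVT or A-fib/flu before use of DL, as they have prevalent disease". Substudy 2B excludes "Individuals with a diagnosis of seizures, epilepsy, prescriptions of antiepileptic medicine, malignant brain tumor, or head trauma before redemption of first DL prescription". Neither exclusion sets a minimum residence or look-back. Section 7.3.2 gives the source: "Information on outcome variables will be obtained from the Nordic national patient registers".

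**Outcome truncation.** Section 7.9 describes it as a matter of when each patient register began: 1977 in Denmark, 1967 in Finland, 1987 in Sweden and 2008 in Norway. For the first three countries it concludes: "Thus, the impact of truncation bias on results from these countries is limited".

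**Emigration.** Under 7.7.2 to 7.7.4, follow-up ends at emigration. Table 4, in the row for country, says instead that people who emigrate are excluded.

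**Data at hand.** Section 7.3.4 says: "We will also obtain information on immigration and emigration, as well as date of birth and death status".

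**The concern.** All three outcomes are first events, and whether an event is a first one is judged from the register. For an immigrant, that history begins on arrival, whatever year the register opened. The protocol sees this for drug use and deals with it. It does not carry the same reasoning over to outcomes, where the consequence is more direct: an old arrhythmia diagnosed abroad can enter the numerator as a new one.

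Such events say nothing about starting DL. Spread evenly over follow-up, they dilute a true association. If they surface soon after entry, when people have just redeemed DL and are in exposed time, they create or inflate one. In a safety study whose null is no association, neither error can be assumed harmless.

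The wording raises a second problem. The rule excludes persons, and it is not limited to the first redemption or the first immigration. Someone who used DL, emigrated, returned and refilled within 6 months would lose all earlier person-time and any earlier event because of something that happened after their follow-up had ended.

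**Working it through.** **1. Look-back that the rule guarantees.** An immigrant who stays in the cohort has no redemption in the first 6 months after arrival and enters at the first recorded redemption. The guaranteed register history is therefore just over 6 months, with no upper limit. By the start years in Table 5, a lifelong resident entering in 2010 can have up to 2010 − 1977 = 33 years (Denmark), 2010 − 1967 = 43 (Finland), 2010 − 1987 = 23 (Sweden) or 2010 − 2008 = 2 (Norway). The 7.9 conclusion that truncation is limited rests on the first three figures, and these do not apply to recent immigrants.

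**2. Screens that remain.** Seizure cases are also screened by antiepileptic prescriptions redeemed after arrival (7.2.2, 7.9). No drug surrogate is listed for SVT or A-fib/flu. In every substudy, a false first event needs two things: no registered diagnosis between arrival and first DL redemption, then a primary emergency-room or inpatient diagnosis (7.3.2).

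**3. Size if false events fall evenly.** The protocol has no figure to reproduce. Let s be the share of users with short residence, h the share of these with unseen old disease, r the yearly rate at which that disease presents, and I the background rate. The false rate is f = s·h·r, and the observed ratio is (IRR·I + f)/(I + f). The values of s, h and r are assumptions; I comes from Tables 7 and 8, age 20–64.

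| Assumed s, h, r | f per 100,000 | f/I, SVT (I = 27) | SVT: true 1.5 becomes | f/I, A-fib (I = 168.9) |
|---|---|---|---|---|
| 2%, 0.2%, 10% | 0.4 | 1.5% | 1.49 | 0.24% |
| 5%, 0.3%, 15% | 2.25 | 8.3% | 1.46 | 1.3% |
| 8%, 0.4%, 20% | 6.4 | 24% | 1.40 | 3.8% |

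Middle row for SVT: (1.5 × 27 + 2.25)/(27 + 2.25) = 42.75/29.25 = 1.46. With evenly spread events, a true ratio of 1 stays at 1.

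**4. Size if timing is allowed for.** A person leaves follow-up at the first counted event, so the pool of unseen disease empties with time. Take exposed time as weeks 0–10 after entry and unexposed time as 6 months to 6 years. This is a simplification that ignores later exposed periods. Then

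- exposed: f_e = s·h·(1 − exp(−r·10/52))/(10/52)
- unexposed: f_u = s·h·(exp(−0.5r) − exp(−6r))/5.5

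and the observed ratio is (IRR·I + f_e)/(I + f_u).

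- Middle inputs (5%, 0.3%, 15%), SVT: f_e = 0.00015 × 0.1479 = 2.22 and f_u = 0.00015 × 0.0948 = 1.42 per 100,000. A true 1.0 becomes 29.22/28.42 = 1.03. A true 1.5 becomes 42.72/28.42 = 1.50, so the two effects cancel.
- s = 5%, h = 0.5%, r = 0.1 per year, SVT: a true 1.0 becomes 1.02, and a true 1.5 becomes 1.49.
- Same s and h, r = 0.5 per year, SVT: a true 1.0 becomes 1.28, and a true 1.5 becomes 1.73.
- A-fib at age 65 or over (I = 2154.3), s from 1% to 10%, h from 0.5% to 2%, r from 0.1 to 0.5 per year: a true 1.0 becomes 1.00 to 1.03.

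The sign of the bias therefore depends on r and on the true ratio, and its size on s and h. The documents give none of these. Where the background rate is high, the effect is negligible.

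**5. The person-level wording.** Sections 7.7.2 to 7.7.4 censor at emigration, which keeps the earlier person-time. Table 4 excludes emigrants, which read literally discards it. The immigrant rule read literally also discards it for a returning resident who refills within 6 months. The last two select person-time on information that does not exist at cohort entry, and they disagree with the first.

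**The case against.** **Most immigrants are better documented than the minimum suggests.** A reader might infer that immigrants as a group enter with almost no outcome history, or that their old disease is always counted as new. The documents do not support that. Just over 6 months is the floor; many will have lived in the country for years before first redeeming DL, and a false event must pass the screens in step 2. This stands, and the point is limited to what can happen.

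**No size or direction can be claimed.** A reader might take step 3 to show that the bias is towards 1, and so understates risk. It does not: that model ignores timing, and step 4 can reverse the sign. All the inputs are assumed. This stands too. It also means that the bias cannot be dismissed as small or conservative.

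**The later-redemption problem is narrow.** A reader might infer that the rule routinely drops people because of later refills. For a first-time immigrant, a redemption in the first 6 months is necessarily the first one recorded, so the exclusion acts at entry, as 7.7.1 and 7.9 intend. Only residents who used DL, emigrated and came back are affected. That makes it a matter of wording, but of wording that determines who is analysed.

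**Comparability with P203.** Section 5 says that the only change to P203's methods is removal of the secondary analyses, and that this report builds on the three-country one. A new entry rule in the main cohort would break that continuity. This is a good reason to keep the main cohort and put the residence restriction in a supplementary analysis.

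**A 5-year window is a covariate window, and Norway stays short.** Both are true. Someone entering in Norway in 2009 after 5 years of residence still has at most about 2 years of hospital history. Section 7.9 already discloses Norway's truncation; the gap is in what it says of the other three countries.

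**Conclusion.** The concern holds in a limited form. The immigrant rule is a wash-out of DL dispensings only, and no other rule secures outcome history for immigrants. Disease diagnosed abroad can therefore be counted as a first event, mainly for SVT and A-fib/flu. The statement in 7.9 that truncation has limited impact in Denmark, Finland and Sweden does not cover them.

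Under the assumed inputs shown, a true SVT ratio of 1.5 at age 20–64 is estimated anywhere from 1.40 to 1.73, and a true null at 1.00 to 1.28. For A-fib at age 65 or over, a true null moves by 0.03 at most. These are illustrations and not estimates, since the share of immigrants, the prevalence of unseen disease and its rate of presentation are all assumed. What is certain is the gap in the rule, together with the conflict between Table 4 and 7.7.2 to 7.7.4 over people who emigrate. Both are worth correcting because the correction is cheap and the effect is otherwise unknowable.

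**What to change.** 1. In 7.7.2 to 7.7.4, apply the 6-month rule once, at the first recorded DL redemption and relative to the latest immigration before it. State that later redemptions and later immigrations do not trigger it. Reconcile the country row of Table 4 with the censoring at emigration.

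2. Keep the main cohort as it is, for comparability with P203. Add to 7.7.5 a supplementary analysis of 2B, 3B and 4B restricted to persons born in the country or resident for at least 5 years before first DL redemption. Five years is the look-back that Table 4 already uses for asthma, severe rhinitis and chronic urticaria, so the restriction lengthens the observed covariate history as well. Note that in Norway hospital history remains limited by the 2008 register start.

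3. In 7.9, name immigration as a source of outcome truncation, and limit the statement about Denmark, Finland and Sweden to people resident there since before the look-back.

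Cost: a few sentences and one additional analysis with slightly fewer users. Section 7.3.4 already provides the immigration and birth dates, so no new data are needed. A clear difference from the main result would show that short residence matters; similar results would give the sponsor evidence that it does not.

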7.7.3 Substudy 3: SVT

Substudy 3A

A cohort study estimating the incidence of SVT in the general population will be performed. The cohort of DL users, the cohort of individuals with SVT, and the distribution of the population by age, year, and country will be used to derive estimates in the general population. The number of individuals in the general population on 01 January of each year will be obtained from the NORDCAN database and used as an estimate of the number of person years at risk assuming each person in the population on 01 January of each year contributes one person year at risk [Association of Nordic Cancer Registries 2009]. The IRs of SVT will be shown for the total population and stratified by country, sex, and age. The confidence interval of IRs is calculated as outlined above under Substudy 2A.

Substudy 3B

A cohort study among ever-DL users analyzing the association between exposed and unexposed time (as defined in Substudy 2B) and first SVT will be performed for the total population and stratified by age. A person who has redeemed at least one prescription of DL is included in the cohort and enters the cohort at the date of first prescription redemption. Study individuals are followed until occurrence of a SVT; 31 December 2015; emigration; or death, whichever comes first. The association between exposure to DL use and first SVT will be evaluated using Poisson regression of the IR of first SVT, and the measure of effect is the IRR. A person with prescription redemption of DL in Norway and Sweden within the first 6 months after establishment of the prescriptions registers will not be included in order to account for truncation bias. In addition we exclude persons with DL prescription redemptions within 6 months after immigrating to Denmark, Finland, Norway, or Sweden. The analyses will be adjusted for confounders identified from the DAG (i.e., country, age, sex, calendar year, seasonality, severity of rhinitis, asthmatic status, and chronic urticaria status) (Table 4). We will evaluate whether age can be included as a continuous variable by examining the assumption of linearity. Alternatively, age will be included as a categorical variable.

